## 1. Introduction

### 1.1 Background on Ebola Virus Infection

Clinical Ebola hemorrhagic fever is characterized by onset of fever, headache, myalgia, fatigue and gastrointestinal distress, 2-21 days post exposure to virus. Immune responses play a critical role in Ebola virus (EBOV) pathogenesis: infection is associated with an early loss of lymphocytes and down-regulation of interferon production and actions. There is subsequent dysregulation of coagulation, leading to clinically important hemorrhage in a minority of patients. The genus *ebolavirus* includes 5 different viruses: Sudan virus, Tai Forest virus, EBOV, Reston virus and Bundibugyo virus. EBOV has the highest fatality rate – 57-90%. Data from human infections with EBOV are limited, but the evidence from previous outbreaks suggests that the innate immune response is predictive of outcome. Specifically, an early and transient pro-inflammatory cytokine response, including IFN- $\alpha$ , is associated with survival, yet a sustained and increasing pro-inflammatory cytokine response, with dendritic cell infection that abrogates the IFN response, is associated with death (1, 2). Notably, in the absence of a robust innate immune response, including IFN- $\alpha$  activation of dendritic cells, the adaptive immune response (B and T cell activation) is severely impaired, leading to failure of control of viral replication and poor outcome.

### 1.2 Epidemiologic situation as of November 19, 2014 (WHO data)

In the context of this outbreak, this is the first outbreak in West Africa, therefore there is a lack of understanding within local communities, lack of experience among health care workers and limited capacity for rapid response. There is a high level of community exposure, a consequence of household care and customary burial procedures, leading to fear, panic and some resistance to proposed response measures. Close community ties across border areas are having an impact on care-seeking behaviors and contact tracing. The magnitude of the spread of this outbreak in the 3 most affected countries, as of November 19, 2014, is in rural areas and in large cities, (see Table 1), and requires an enormous commitment of resources and robust sustained response capacity.

There is no vaccine or specific approved treatment for EBOV disease currently available. At the present time, patients are only provided with usual supportive care on arrival at treatment centres. There are promising data related to novel vaccines and potential antiviral drugs, derived from *in vitro* and pre-clinical animal models of EBOV infection, yet these have not been evaluated for safety and efficacy in humans.

In the current context, the WHO has recommended that it is ethical to offer unproven interventions (with unknown efficacy and unknown adverse events) as potential treatments or prevention strategies. Any therapeutic intervention must be administered with informed consent and freedom of choice, the decision having been made following a thorough risk-benefit assessment, and respecting the confidentiality and dignity of the patient. In addition, there is a moral obligation to collect and share all data generated, to understand the safety and efficacy of any intervention, including a moral duty to evaluate any intervention in the best possible clinical trial feasible, and to inform future interventions.

Country	Cumulative cases (Conf-Prob)	Cumulative deaths
Guinea	2047	1214
Liberia	7082	2963
Sierra Leone	6190	1267

**Table 1**

### **1.3 WHO Working Group to Evaluate Lead Experimental Therapeutic Intervention Candidates: outcomes**

In late August 2014, a WHO-initiated Working Group was assembled to consider the various experimental therapeutic intervention candidates for EBOV disease. Early during the deliberations the decision was made to evaluate only those candidates that have been evaluated in pre-clinical rodent and nonhuman primate models of EBOV disease.

Vaccine candidates for general use pre-exposure and post-exposure prophylaxis included the vesicular stomatitis virus/Ebola Zaire glycoprotein vaccine (NewLink/Public Health Agency of Canada), requiring -80° to -20°C storage, for which there are currently 800 doses available and has been evaluated in nonhuman primates. A number of other candidate vaccines were considered, lacking nonhuman primate efficacy data, GMP manufactured product and or other nonclinical studies. Notably, the Crucell ChAd3 adenovirus vaccine is poised to be evaluated in Phase 1 studies in the Gambia and Mali in late September 2014, with projected availability of 15,000 doses of vaccine for Phase 2 studies in December, 2014.

Candidate antiviral therapeutic interventions were also evaluated. These included antiviral agents that may target the virus directly, may target a host function required for the viral life cycle and/or may augment host defenses. With the exception of USFDA-approved drugs that are being considered for repurposing as antivirals against EBOV disease, all of the other antiviral agents considered are under development. Actual treatment doses and regimens are uncertain at the current time and the mechanism of action of individual agents will dictate their temporal usage (early vs. late stage disease).

#### 1.4 Candidate Therapeutic Interventions

**ZMapp** (LeafBio) is produced in tobacco plants, is a triple monoclonal antibody cocktail, with a mechanism of action that neutralizes the virus and kills infected cells. Nonhuman primate studies revealed 100% treatment efficacy when treatment was initiated 5 days after virus infection. There are no controlled human safety data and no product currently available.

**Human convalescent serum** There is limited nonhuman primate efficacy study data that suggest passive transfers may provide partial protection. An ISARIC protocol for convalescent plasma collection and administration is under development. The availability and feasibility of administration of convalescent serum is location-dependent, i.e. available infrastructure to collect, process, and screen.

**Antibody infusions** Equine F(ab)2 (Fabentech, France) and Transchromosomal cattle human polyclonal antibody (Sanford Applied Biologics, USA) are under development, with projected availability in 6 months.

**TKM-100802** (Tekmira Pharmaceuticals) is a cocktail of 2 small interfering RNAs (siRNAs) in lipid nanoparticle, targeting the viral proteins VP35 and L Polymerase, thereby silencing the viral genes and preventing viral replication. In nonhuman primate studies there was evidence of 83% treatment efficacy when initiated 48 hours after virus infection, and 67% treatment efficacy when initiated 72 hours post infection. Phase 1 single ascending dose studies have been completed. Storage of drug is at room temperature. Currently there are 30 treatment courses available with a projected 54 treatment courses to be available in 3.5 months and 490 in 6 months.

**AVI-7537** (Sarepta) is a phosph morpholino oligonucleotide that blocks viral protein production. Nonhuman primate studies showed 60-80% efficacy when treatment was initiated at 1 hour post infection. Phase 1 single ascending doses studies have been completed. Treatment course is 14 days with room temperature storage of drug. Potential availability of 24 treatment courses by mid-October is projected.

**Favipiravir** (T-705) (Medivector/Toyma/Fuji) is a small molecule, viral polymerase inhibitor that has been conditionally approved in Japan for influenza virus infection. Published *in vitro* and mouse model studies suggest that the drug is anywhere from 10-60 fold less effective against EBOV than influenza virus. Pilot nonhuman primate studies are underway with anticipated higher dosing. Up to 15,000 treatment courses are currently available, with a projected 100,000 treatment courses to be available in 3 months. It is anticipated that 90 tablets are required over 5 days for human treatment course. Given the high incidence of nausea, vomiting and diarrhea in EBOV-infected individuals, this oral bioavailability presents a significant concern.

**BCX4430** (BioCryst Pharmaceuticals, Inc.) is a small molecule, viral polymerase inhibitor. Efficacy has been demonstrated *in vitro* and in mouse models of EBOV disease. Nonhuman primate studies are anticipated to begin shortly. A preclinical IND submission is anticipated in November 2014, with potentially 2000 treatment courses projected to be available in March 2015.

**Brincidofovir** (CMX001) (Chimerix) is a small molecule, viral polymerase inhibitor that has demonstrated *in vitro* antiviral activity against filoviruses. Because of metabolism differences its evaluation in Macaque nonhuman primates is precluded. Phase 3 studies in >1000 trial subjects have been conducted against CMV and adenovirus infections. Potentially there are 3,500 treatment courses currently available. Oral bioavailability given nausea, vomiting, and diarrhea is a concern for the 6-10 tablet treatment course.

**Coagulation related interventions** Recombinant nematode anti-coagulant protein C2 that blocks Factor X cleavage has completed Phase 2 trials. The drug exhibits 33% efficacy when initiated 24 hours after infection in nonhuman primates. 100 doses are currently availability, dependent on ongoing stability testing. Drotrecogin alfa was approved for the treatment of severe sepsis, but has been withdrawn. Nonhuman primate studies showed 18% treatment efficacy when administered <6 hours after infection. Availability is unknown.

### 1.5 Repurposing Approved Drugs

Given the poor availability and logistics/feasibility surrounding administration of some of the candidate interventions evaluated above, the repurposing of approved drugs was evaluated. Advantages include availability and clinical experience with these drugs. Briefly, these included Clomiphene/Toremifene, selective estrogen receptor modulators that may have an effect on late viral entry and have some demonstrated *in vitro* efficacy, also affording 90% survival when administered 1 hour after infection of mice. However, nonhuman primate studies identified ocular disturbances that resulted to studies being suspended while these adverse events are investigated. *In vitro* screens of libraries of drugs have identified a number of candidates, including ion channel inhibitors, kinase inhibitors, anti-parasitic drugs and anti-inflammatory drugs, however additional studies are needed to further evaluate the potential of these interventions in EBOV disease.

#### 1.5.1 Interferon

Interferons (IFNs) are classified as type I (IFNs- $\alpha$ , - $\beta$ , - $\omega$ , - $\tau$  - $\kappa$ , - $\epsilon$ ,  $\xi$ , type II (IFN- $\gamma$ ) or type III (IFNs- $\lambda$ : IL-28A, IL-28B, IL-29). Type I IFNs mediate diverse biological effects, including the largely species-specific but cell type-independent antiviral responses, and several cell type-restricted responses of immunological relevance. IFNs modulate both T and B lymphocyte responses by promoting the proliferation of memory T cells, promoting the differentiation of Th1 cells, inducing IFN- $\gamma$  secretion from T cells, and promoting isotype switching in B cells and differentiation into plasma cells. IFNs- $\alpha/\beta$  upregulate MHC class I. Moreover, IFNs activate macrophages, activate and enhance the cytotoxicity of NK cells, and regulate the maturation and terminal differentiation of dendritic cells. IFNs have widespread potential as therapeutic agents for the treatment of viral infections, and are currently administered for chronic hepatitis B and C (HCV) infections. IFNs inhibit viral infection by preventing viral entry into target cells and by blocking different stages of the viral replicative cycle for different viruses. Type I IFNs have a critical role in linking the innate and adaptive immune responses to viral challenge. IFNs- $\alpha/\beta$  regulate the activities of other cytokines and their receptors, including IFN- $\gamma$ , IL-1, IL-1 receptor, IL-2, IL-3, IL-8, TNF- $\alpha$ , IL-18 etc, and chemokines such as CCL3, CCL4, CCL5, and the chemokine receptor, CCR5.

IFN- $\alpha/\beta$  expression occurs as the earliest non-specific response to viral infection, mediated by activation of microbial pattern recognition receptors including TLRs and cytoplasmic receptors RIG-I/MDA5, preceding other cytokines. Indeed, viruses have evolved immune evasion strategies specifically targeted against an IFN response, confirming the importance of IFNs as antivirals.

[figure not shown]
This immune evasion strategy is relevant when one considers IFN treatment for EBOV infection (3, 4). Experimental data indicate that EBOV proteins VP24 and VP35 inhibit host cell systems that lead to IFN production and also inhibit events associated with an IFN response. EBOV VP35 effectively blocks IFN- $\alpha/\beta$  production by either RIG-I or MDA5 (5). Indeed, specific effector molecules of an IFN response have been shown to directly inhibit EBOV entry into cells and release of viral progeny from cells, effectively preventing viral spread. Treating EBOV infected individuals with IFN may therefore override the inhibitory effects of EBOV infection on IFN *production*, but the challenge remains to administer treatment early post-exposure, before the viral burden is such that IFN responsiveness would be disabled.

IFN- $\alpha 2$  has been approved by the USFDA for the treatment of AIDS-related Kaposi's Sarcoma, and hepatitis B. In combination with ribavirin, different IFN- $\alpha 2$  preparations and Infergen (IFN- $\alpha$ con-1) have been approved by the USFDA for hepatitis C infection (and are currently being evaluated in HIV infection). Estimates of 40% sustained virologic response against HCV genotype 1 and 70% against genotypes 2 and 3, using the pegylated IFN- $\alpha$ s in combination with ribavirin, provide evidence for the therapeutic benefits of IFNs- $\alpha$  as antivirals. IFN- $\alpha$  has also been shown to have anti-inflammatory effects by decreasing cell proliferation and increasing circulating levels of TNF- $\alpha$ -receptor. Thus IFN- $\alpha$ s have been demonstrated clinically to have a role in treating viral diseases.

Notably, in all the nonhuman primate studies where either an IFN- $\beta$  or an IFN- $\alpha$  or the adenoviral vectored-Infergen gene was administered, there are 3 considerations that may account for the limited therapeutic benefit that was observed: 1. The challenge dose of EBOV was 1000 PFU by intramuscular route of inoculation. Both the route of inoculation and the significantly high lethal challenge dose may distinguish course of infection in the nonhuman primates compared with the current human EBOV disease. Of note, the illness in nonhuman primates is more rapid in progression and more lethal than that seen in humans. 2. IFN dosing. In contrast to current dosing for therapeutic efficacy against HCV (and for multiple sclerosis), dosing regimens employed for these published nonhuman primate studies were of the order of 10-100 fold greater (mg/kg). This raises the issue of invoking adverse events that may undermine the potential therapeutic benefit of dosing that might reflect what will be used in humans i.e. survival may have been compromised in these studies. 3. Differences in the innate and adaptive immune responses between nonhuman primates and humans. While some of the rhesus IFN- $\alpha$  subtypes are homologous to the corresponding human sequences (IFN- $\alpha$ 1/13,  $\alpha$ 2,  $\alpha$ 6,  $\alpha$ 8,  $\alpha$ 14, and  $\alpha$ 16), 7 others have a partial homology to human IFN- $\alpha$ 4,  $\alpha$ 16, or  $\alpha$ 21, and have been termed IFN- $\alpha$ 23 to IFN- $\alpha$ 29 (11). TLR7 and TLR9 agonists mediate distinct type I IFN responses in humans and nonhuman primates *in vitro* and *in vivo* (12). Differences in Th1 and Th2 cytokine profiles between humans and nonhuman primates also exist (13). Nonhuman primates are more sensitive to vaccines than humans (14).

## 2. Background on Investigational Product

IFN  $\beta$ -1a is a 166 amino acid glycoprotein with a molecular weight of approximately 22,500 Daltons. It is produced by recombinant DNA technology using genetically engineered Chinese Hamster Ovary cells into which the human interferon beta gene has been introduced.

The amino acid sequence of IFN  $\beta$ -1a is identical to that of natural human IFN  $\beta$ .

Using the World Health Organization (WHO) International Standard for Interferon, the study drug has a specific activity of approximately 200 million international units of antiviral activity per mg of IFN  $\beta$ -1a determined using an *in vitro* cytopathic effect bioassay using lung carcinoma cells (A549) and Encephalomyocarditis virus (EMCV).

30 mcg contains approximately 6 million international units of antiviral activity using this method. The activity against other standards is not known. Comparison of the activity of BiogenIdec's IFN  $\beta$ -1a with other IFNs  $\beta$  is not appropriate because of differences in the reference standards and assays used to measure activity.

## 2.1 Rationale for Choice of IFN $\beta$ Preparation

1. Data from published and unpublished nonhuman primate studies suggest that IFN  $\beta$ -1a treatment may be more effective in reducing viremia and prolonging survival than IFN- $\alpha$ .
2. Availability of pre-filled syringes of IFN  $\beta$ -1a.

In addition, the following supports the choice of IFN  $\beta$ -1a:

Like other members of the Type I IFN family, IFN  $\beta$ -1a has been shown to protect cells from virus infection, as well as showing efficacy in HCV-infected individuals (15). Moreover, while IFN- $\alpha$  has been used to treat HCV in Europe and the US, natural, non-recombinant IFN- $\beta$  has been used extensively in Japan for this indication, and there is data to suggest that in HCV, where both IFN- $\alpha$  and IFN- $\beta$  have been used to treat the disease, that the safety and tolerability of IFN- $\beta$  is more favorable than for IFN- $\alpha$  (16, 17). In addition to the known antiviral activity of IFN  $\beta$ -1a in HCV and its antiviral activity in Ebola-infected rhesus macaques (6), AVONEX has a favorable safety and tolerability profile in MS patients with approximately 1.9 million person years of exposure worldwide (BiogenIdec Inc., data on file).

## 2.2 Clinical Experience with AVONEX in multiple sclerosis

The clinical effects of AVONEX in patients with relapsing forms of multiple sclerosis (MS) were studied in two randomized, multicenter, double-blind, placebo-controlled studies in patients with MS (Studies 1 and 2). Safety and efficacy of treatment with AVONEX for over 10 years has been studied.

In Study 1, 301 patients received either 30 mcg of AVONEX (n=158) or placebo (n=143) by intramuscular injection once weekly. Patients received injections for up to 2 years, and continued to be followed until study completion. Two hundred eighty-two patients completed 1 year on study, and 172 patients completed 2 years on study. There were 144 patients treated with AVONEX for more than 1 year, 115 patients for more than 18 months and 82 patients for 2 years.

All patients had a definite diagnosis of multiple sclerosis of at least 1 year duration and had at least 2 exacerbations in the 3 years prior to study entry (or 1 per year if the duration of disease was less than 3 years). At entry, study participants were without exacerbation during the prior 2

months and had Kurtzke Expanded Disability Status Scale (EDSS) scores ranging from 1.0 to 3.5. The EDSS is a scale that quantifies disability in patients with MS and ranges from 0 (normal neurologic exam) to 10 (death due to MS). Patients with chronic progressive multiple sclerosis were excluded from this study.

The primary outcome assessment was time to progression in disability, measured as an increase in the EDSS score of at least 1 point that was sustained for at least 6 months. An increase in EDSS score reflects accumulation of disability. This endpoint was used to help distinguish permanent increase in disability from a transient increase due to an exacerbation.

The time to onset of sustained progression in disability was significantly longer in AVONEX-treated patients than in placebo-treated patients in Study 1 ( $p = 0.02$ ). The percentage of patients progressing by the end of 2 years was 35% for placebo-treated patients and 22% for AVONEX-treated patients. This represents a 37% relative reduction in the risk of accumulating disability in the AVONEX-treated group compared to the placebo-treated group.

The distribution of confirmed EDSS change from study entry (baseline) to the end of the study was examined. There was a statistically significant difference between the AVONEX and placebo groups in confirmed change for patients with at least 2 scheduled visits ( $p = 0.006$ ).

The rate and frequency of MS exacerbations were secondary outcomes. For all patients included in the study, irrespective of time on study, the annual exacerbation rate was 0.67 per year in the AVONEX-treated group and 0.82 per year in the placebo-treated group ( $p = 0.04$ ).

AVONEX treatment significantly decreased the frequency of exacerbations in the subset of patients who were enrolled in the study for at least 2 years (87 placebo-treated patients and 85 AVONEX-treated patients;  $p = 0.03$ ).

Gadolinium (Gd)-enhanced and T2-weighted magnetic resonance imaging (MRI) scans of the brain were obtained in most patients at baseline and at the end of 1 and 2 years of treatment. Secondary outcomes included Gd-enhanced lesion number and volume, and T2-weighted lesion volume. Gd-enhancing lesions seen on brain MRI scans represent areas of breakdown of the blood brain barrier thought to be secondary to inflammation. AVONEX-treated patients demonstrated significantly lower Gd-enhanced lesion number after 1 and 2 years of treatment than placebo-treated patients ( $p < 0.05$ ). The volume of Gd-enhanced lesions showed similar treatment effects in the AVONEX and placebo groups ( $p < 0.03$ ). Percentage change in T2-weighted lesion volume from study entry to Year 1 was significantly lower in AVONEX-treated than placebo-treated patients ( $p = 0.02$ ). A significant difference in T2-weighted lesion volume change was not seen between study entry and Year 2 in the AVONEX and placebo groups.

The exact relationship between MRI findings and the clinical status of MS patients is unknown. The prognostic significance of MRI findings in these studies has not been evaluated.

In Study 2, 383 patients who had recently experienced an isolated demyelinating event involving the optic nerve, spinal cord, or brainstem/cerebellum, and who had lesions typical of multiple sclerosis on brain MRI, received either 30 mcg of AVONEX ( $n = 193$ ) or placebo ( $n = 190$ ) by intramuscular injection once weekly. Patients were enrolled into the study over a two-year period and followed for up to three years or until they developed a second clinical exacerbation

in an anatomically distinct region of the central nervous system.

In Study 2, the primary outcome measure was time to development of a second exacerbation in an anatomically distinct region of the central nervous system. Time to development of a second exacerbation was significantly delayed in AVONEX-treated compared to placebo-treated patients ( $p = 0.002$ ). The Kaplan-Meier estimates of the percentage of patients developing an exacerbation within 24 months were 39% in the placebo group and 21% in the AVONEX group. The relative rate of developing a second exacerbation in the AVONEX group was 0.56 of the rate in the placebo group (95% confidence interval 0.38 to 0.81).

## **2.3 Safety Considerations of IFN $\beta$ -1a**

### **2.3.1 Potential Risks**

Depression, Suicide, and Psychotic Disorders.

Hepatic Injury: monitor liver function tests; monitor patients for signs and symptoms of hepatic injury; consider discontinuation of IFN  $\beta$ -1a if hepatic injury occurs.

Anaphylaxis and Other Allergic-Reactions: Discontinue if occurs.

Congestive Heart Failure: monitor patients with pre-existing significant cardiac disease for worsening of cardiac symptoms.

Decreased Peripheral Blood Counts: monitor complete blood count.

Autoimmune Disorders: consider discontinuation of IFN  $\beta$ -1a if new autoimmune disorder occurs.

The most common adverse reactions (at least 5% more frequent on AVONEX than on placebo) were flu-like symptoms including chills, fever, myalgia, and asthenia.

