### **Rare Adverse Events (<1% frequency)**

Severe psychiatric adverse events may develop in persons receiving therapy with IFN  $\beta$ -1a and includes suicidal ideation and suicide. The risk of this happening is small and less than 1%.

IFN- $\alpha/\beta$  has on occasion exacerbated pre-existing cardiovascular disease, and has caused angina (chest pain), rhythm disturbances or heart attacks (myocardial infarction) in these persons. In those with known pre-existing heart disease, physicians will monitor for cardiac symptoms closely and discontinue IFN  $\beta$ -1a if cardiovascular symptoms appear to be worsened by the drug.

IFN  $\beta$ -1a has rarely been associated with ophthalmic problems, including retinal hemorrhages, optic neuritis and papilledema in persons on long-term treatment. Participants will be asked to report to their physician any disturbance in vision while they are on treatment.

IFN  $\beta$ -1a may exacerbate liver disease and will be discontinued with grade 4 hepatotoxicity.

Very rarely IFN  $\beta$ -1a has been associated with pulmonary syndromes including pneumonia and worsening of asthma. If a participant develops worsening pulmonary symptomatology, which is felt to be due to IFN  $\beta$ -1a then the drug will be dose-reduced or stopped.

IFN  $\beta$ -1a may aggravate autoimmune diseases (for example, systemic lupus or rheumatoid arthritis), and those with pre-existing autoimmune disease will be closely monitored.

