### **Management of Adverse Events**

Management of adverse events is generally achieved by dose reduction of IFN  $\beta$ -1a, however, in the case of life-threatening adverse events, development of cardiac dysfunction, or precipitous decline in pulmonary function over a 24 hour period, which is not explained by disease progression and which may be associated IFN  $\beta$ -1a, therapy will be discontinued.

Flu-like symptoms can be treated with acetaminophen 500-1000 mg or ibuprofen 200-400 mg 30 minutes before IFN  $\beta$ -1a injection.

The following guidelines will be used to determine when dose modification of the investigational product for an adverse event should be implemented.

- Grade I (mild) adverse events: No dosage adjustment
- Grade 2 (moderate) adverse events: No dosage adjustment
- Grade 3 (severe) adverse events: Patients who develop grade 3 adverse events (except flu like symptoms, unless they are incapacitating) should have IFN  $\beta$ -1a reduced to 3 MIU (15 mcg). Alternatively, IFN  $\beta$ -1a may be discontinued.

- Grade 4 (Life threatening) adverse events (SAE): IFN  $\beta$ -1a will be discontinued.

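### The Section 8.2 grade list leaves the dose unchanged at grades 1-2, but Section 2.3.1 (allergic reactions) and the rare-event text of 8.2 (cardiac, pulmonary) require action whatever the grade, and no text says which prevails

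*Protocol*

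**What the plan says.** Three places in the protocol tell the physician what to do with IFN β-1a after an adverse event.

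- **Section 2.3.1, Potential Risks.** For allergy: "Anaphylaxis and Other Allergic-Reactions: Discontinue if occurs". The word covering reactions other than anaphylaxis means that it is not confined to severe ones. For heart failure the section asks only for monitoring. For liver injury it asks that stopping be considered. It has no pulmonary rule.
- **Section 8.2, Rare Adverse Events.** In patients with known heart disease the drug is stopped "if cardiovascular symptoms appear to be worsened by the drug". For pulmonary worsening attributed to interferon, "then the drug will be dose-reduced or stopped". For the liver, IFN β-1a "will be discontinued with grade 4 hepatotoxicity". Only the hepatic rule names a grade.
- **Section 8.2, Management of Adverse Events.** A lead-in sentence first makes an exception to management by dose reduction. Therapy is discontinued for life-threatening events, for new cardiac dysfunction and for a precipitous 24-hour fall in pulmonary function, where disease progression does not explain them and the drug may. The list follows: "Grade I (mild) adverse events: No dosage adjustment"; "Grade 2 (moderate) adverse events: No dosage adjustment"; "Patients who develop grade 3 adverse events (except flu like symptoms, unless they are incapacitating) should have IFN" β-1a cut to 3 MIU, with discontinuation as an alternative; and "Grade 4 (Life threatening) adverse events (SAE): IFN" β-1a is discontinued. The only event type excepted within the list is flu-like symptoms at grade 3.

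The Adverse Events text of Section 8.2 describes itself as supplementing Section 2.3, so the sections are meant to be read together. Section 6.3 places dose adjustments with the treating physician.

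**The concern.** The list is introduced as what will be used to decide on dose modification, and it depends on grade alone. The allergic, cardiac and pulmonary rules depend on the kind of event and, for the last two, on attribution to the drug. They carry no grade. A mild or moderate event of one of these kinds falls under both sets of rules, and the two sets give different actions.

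What is at stake is consistent handling of a recognised risk. Section 3 foresees more than one centre. Two physicians following the protocol faithfully could treat the same mild allergic reaction in opposite ways, one continuing and one stopping, and each could point to a sentence that supports the decision. Neither action could then be classed clearly as a protocol deviation.

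**Working it through.** The plan gives no figure on this point, so the check is a comparison of the rules grade by grade. The inputs are the grade list and its lead-in (Section 8.2, Management of Adverse Events), the cardiac, pulmonary and hepatic rules (Section 8.2, Rare Adverse Events) and the allergic and hepatic rules (Section 2.3.1).

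| Event | Event-specific rule | List, grades 1-2: no change | List, grade 3: reduce or stop | List, grade 4: stop |
|---|---|---|---|---|
| Allergic reaction | Stop, any grade | Conflict | Reduction option inconsistent; stopping satisfies both | Agree |
| Cardiovascular symptoms that seem worsened by the drug, known heart disease | Stop, any grade | Conflict, unless the lead-in applies | Reduction option inconsistent; stopping satisfies both | Agree |
| Pulmonary worsening attributed to interferon | Reduce or stop, any grade | Conflict, unless the lead-in applies | Agree | Stopping satisfies both |
| Hepatic | Consider stopping (2.3.1); stop at grade 4 (8.2) | Tension only: to consider is not to require | Agree: the list already allows stopping | Agree |

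**Count.** Three event types with an ungraded mandatory rule by four grades gives 3 × 4 = 12 combinations.

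- Outright conflict, where no single action satisfies both texts: 3 event types × 2 grades (1 and 2) = 6.
- Partial inconsistency, where one option in the list is barred by the event rule: allergic and cardiac at grade 3 = 2.
- An action exists that meets both texts, with no option of the list barred: 12 − 6 − 2 = 4.

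**Effect of the lead-in.** It covers life-threatening events, cardiac dysfunction and precipitous pulmonary decline, so it can take some cardiac and pulmonary cases out of the list. It does not reach worsened cardiovascular symptoms short of dysfunction or slower pulmonary worsening. It does not mention allergic reactions at all. The two allergic combinations at grades 1-2 therefore stand without qualification, and the four cardiac and pulmonary ones stand outside the lead-in.

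**Possible actions for one patient at grades 1-2.** Allergic: continue or stop. Cardiac: continue or stop. Pulmonary: continue, reduce or stop.

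**The case against.** The best defence is that this is a general rule with specific exceptions. Section 8.2 says that events are generally handled by dose reduction, calls the list guidelines, and introduces exceptions before it. The cardiac and pulmonary rules stand just ahead in the same section. They are narrow, limited to known heart disease or to worsening attributed to interferon, whereas the list covers any event of any cause. Reading the narrow rule as qualifying the broad one is natural. Section 6.3 gives dose adjustments to the treating physician, and Sections 8.1 and 8.2 allow reduction or stopping without a grade when worsening of the disease is thought to be drug-related. Section 5.4 also excludes known hypersensitivity to interferon beta and grade III or IV heart failure, although the physician may review those exclusions.

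Part of this stands. The exceptions reading is reasonable for cardiac dysfunction and precipitous pulmonary decline, because the lead-in says so. For the remaining cases the protocol does not say that the specific rule prevails, and the list names one exception of its own without naming these. Physician responsibility says who decides, not which of two instructions governs. The Section 8.1 provision and the corresponding one in 8.2 concern worsening Ebola disease, not allergic reactions. The exclusions shrink the groups at risk but do not prevent a first allergic reaction.

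A reader might infer more than the text supports:

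- That 8 of the 12 combinations are strict conflicts. At grade 3 a physician who stops complies with both texts, so the strict count is 6.
- That the hepatic rules contradict each other. Section 2.3.1 only asks that stopping be considered, and the Section 8.2 grade 4 rule matches the list.
- That Section 2.3.1 itself has cardiac or pulmonary stopping rules. It has neither.
- That every such patient could be continued, reduced or stopped. Only pulmonary events at grades 1-2 show all three.
- That allergic events are bound to be found because rash is solicited in Section 9.2. The protocol does not link rash to allergy.

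**Conclusion.** The protocol is wrong as written on this point. For an allergic reaction of grade 1 or 2, Section 2.3.1 and the Section 8.2 list give opposite instructions. For drug-worsened cardiovascular symptoms in known heart disease and for pulmonary worsening attributed to interferon, Section 8.2 disagrees with itself at the same grades, except where the lead-in applies. At grade 3 only the reduction option is inconsistent, and only for allergic and cardiac events.

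The 6 of 12 counts combinations of rules, not patients. The documents give no rate for these events in this population, so the number of the planned 30-50 patients affected cannot be estimated. A reader might also infer that the viral-load result would be distorted. Nothing in the documents allows the size of such an effect to be worked out, and it is not claimed here. The conclusion assumes that the list applies to every adverse event, as its wording implies, and that Sections 2.3 and 8.2 are read together, as Section 8.2 indicates.

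**What to change.** The sponsor should reconcile Section 2.3.1, the Rare Adverse Events text of Section 8.2 and the Management of Adverse Events text of Section 8.2. One workable form is a single table with event types as rows and grades as columns, incorporating the lead-in exceptions and any attribution condition, with a sentence stating whether the event-specific rules or the grade list prevails when they differ. The other places can then refer to the table. The hepatic wording can be aligned in the same edit. Which action belongs in each cell is for the sponsor and clinicians to decide, and no view is given here.

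The cost is a protocol edit, with whatever approval the sponsor's amendment process requires. It adds no procedures, visits or samples.
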